COMIRB Protocol

COLORADO MULTIPLE INSTITUTIONAL REVIEW BOARD
[name] [contact] [contact]

Protocol #: 17-0827

Project Title: Validation Study of the WatchPAT 200 in the Diagnosis of Obstructive Sleep Apnea in Children 4-12 Years of Age

Principal Investigator: [name]

Version Date: 01Jun2017

I. Hypotheses:

We hypothesize that the WatchPAT™ 200U (Peripheral arterial tonometry recorder; Itamar Medical, Caesarea, Israel), which is a wrist worn, non-invasive, ambulatory sleep recorder device based on peripheral arterial tone (PAT) signal, pulse rate, actigraphy and pulse oximetry will be able to detect obstructive sleep apnea in children 4 to 12 years of age as effectively as an overnight, attended, in-laboratory polysomnogram.

Our Specific Aims:

1. To evaluate the accuracy of the WatchPAT 200 device compared to an in-laboratory polysomnogram (PSG) in detecting obstructive sleep apnea (OSA) through measurement of the peripheral arterial tone apnea hypopnea index (PAHI) in children 4-12 years of age who are referred to the Children's Hospital Colorado (CHCO) sleep lab for a diagnostic PSG due to concerns for possible OSA.
2. To evaluate the diagnostic agreement of the WatchPAT 200 device in detecting between normal sleep and mild (≥ 2 events per hour) versus moderate to severe obstructive sleep apnea (OAHI of ≥ 5 events per hour) in children 4-12 years of age compared to an in-laboratory PSG.
3. To evaluate the accuracy of the WatchPAT 200 device in measuring other parameters such as the PAT Respiratory disturbance index (PRDI), oxygen desaturation index (ODI), heart rate and body position compared to an in-laboratory PSG.
4. To evaluate the accuracy of the WatchPAT 200 device in determining sleep architecture compared to an in-laboratory polysomnogram.

II. Background and Significance:

Obstructive sleep apnea is estimated to affect approximately 1% to 5% of children between the ages of 5 to 13 years.¹⁻⁴ The morbidity associated with OSA in children is well studied and includes neurobehavioral and cognitive problems, poor school performance, impaired language skills, inattention, hyperactivity and reduced quality of life.⁵⁻¹⁰ Other morbidities include insulin resistance, elevated inflammatory markers, systemic hypertension and in severe cases, left or right ventricular failure and cor pulmonale.¹¹⁻¹⁷ Given these medical consequences, it is very important to screen children and diagnose OSA in a timely manner, especially if there is a high suspicion.

The American Academy of Pediatrics recommend that all children should be screened for snoring. Early identification of OSA is important because of its prevalence in school age children, alleviation of current symptoms once diagnosed and treated, improvement of quality of life, prevention of sequelae, education of parents, and decreased health care utilization.¹ History and physical examination alone has been shown to have poor sensitivity and specificity¹⁸⁻¹⁹; therefore, objective testing is needed.

The American Academy of Pediatrics (AAP)¹ recommends an overnight, attended, in-laboratory polysomnogram (level 1 sleep study) as the diagnostic test of choice for children with suspected OSA. The polysomnogram measures a number of physiologic functions overnight which includes an EEG, pulse oximetry, oronasal airflow, abdominal and chest wall movements, partial pressure of carbon dioxide (PCO₂) and video recording which will help demonstrate the presence or absence of OSA.²⁰ Specific pediatric measuring and scoring criteria are used.²¹

While the polysomnogram is considered a painless, noninvasive procedure by most adults, it can be challenging and even frightening for some children.²² Moreover, it is expensive and the studies are time and labor-intensive to record, score, and interpret. Availability is often limited, and wait times can be long in some regions, especially for infants and young children.^{23,24,25} The AAP clinical practice guideline also suggests ordering an alternative test (or referral to a sleep specialist or otolaryngologist) when an inpatient polysomnogram is not available, with the rationale that some objective testing is better than none.¹

For these reasons, healthcare providers and researchers have looked into alternative objective tests in diagnosing OSA in children. However, these alternative tests (i.e. level 3 sleep study, nap test, overnight continuous pulse oximetry, audiotapes and videotapes, etc.) have been found to have a low negative predictive value, indicating that a negative result is not sufficient to exclude OSA, and the tests should not be used in routine practice.^{1,26}

One of these alternative tests is a level 3 sleep study which records a minimum of four channels, including ventilation, oximetry, ECG, or heart rate, and is done at home or outside of the sleep laboratory, unattended.²⁷ This test has been used in some adults; however, it does not usually record sleep, is not routinely utilized in children, and is not the standard of care in this age group. Therefore, a continued search for alternative testing is needed.

A viable alternative to the polysomnogram is the WatchPAT 200. This is an FDA approved wrist worn ambulatory sleep study device in patients ≥ 12 years of age that uses peripheral arterial tonometry in conjunction with pulse oximetry and actigraphy to assess respiratory disturbances.²⁸ It has 6 channels which includes the following: 1. Peripheral arterial tone (PAT) which measures the arterial volume changes, reflecting sympathetic nervous system activation caused by respiratory disturbances during sleep; 2. Oximetry; 3. Actigraphy, which measures body movement during sleep; 4. Heart rate; 5. Body position, which can measure supine, prone or side sleeping positions and 6. Snoring intensity. Clinical parameters measured include: 1. PAT apnea-hypopnea index (PAHI), 2. PAT respiratory disturbance index (PRDI), 3. PAT sleep staging identification (PSTAGES) and optional snoring level and body position discrete states from an external integrated snoring and body position (SBP) sensor.²⁸

The technology is based on the pathophysiologic mechanism of obstruction-induced transient elevations of sympathetic tone which have been associated with arousals from sleep.²⁹⁻³⁵ The device then indirectly detects apnea and hypopnea via selectively measuring peripheral arterial volume changes mediated by alpha-adrenergic receptors in smooth muscle via a finger mounted plethysmograph. This information is collected together with data from the pulse oximeter and heart rate, which is further analyzed using a predeveloped automated algorithm.³⁶

It requires minimal cleaning, preparation and handling before or after patient use. Fully automated reports are also generated within minutes; thereby helping increase workflow efficiency and hopefully diagnose and treat patients in a more timely manner. Furthermore, it has the advantage of eliminating interscorer variability. This technology has the potential to be an accurate and safe alternative in diagnosing OSA in the younger age group, where the disease is known to be prevalent.

III. Preliminary Studies/Progress Report:

There have been validation studies which were mostly performed in adult patients. Weimin et al. studied 28 adults with suspected OSA who underwent an inpatient polysomnogram while wearing a WatchPAT 200. The study showed comparable accuracy in detecting OSA based on AHI (mean PSG score for events/hour was 23 ± 21.55 compared to a mean score of 25.00 ± 19.09 for the WatchPAT, $r=0.92$, $P<0.001$). It also provided a reasonably accurate estimation of sleep and wakefulness (agreement was $89\pm6\%$).³⁷ In another validation research using the WatchPAT200, Gan et al studied 20 patients with suspected OSA who also had simultaneous PSG and WatchPAT200 concurrently at the sleep lab. The study showed the WatchPAT being 100% sensitive when compared to PSG for detecting mild OSA and concluded that it is a good screening test for the undiagnosed general population. They study showed 100% specificity when compared to PSG for severe OSA suggesting that it is a good diagnostic test for people with a high suspicion of OSA.³⁸

A meta-analysis by Yalamanchali et al. on 14 studies assessing the correlation of sleep indexes between PAT devices and PSG in adults (aged >18 years). The researchers found high overall correlation of the RDI and AHI ($r=0.889$ [95% CI, 0.862-0.911]; $P<.001$). Studies comparing the RDI between PAT and PSG had a combined correlation of 0.879 (95% CI, 0.849-0.904; $P < .001$); those comparing the AHI, 0.893 (0.857-0.920; $P < .001$); and those comparing the ODI, 0.942 (0.894-0.969; $P < .001$).³⁶

Hedner et al. specifically studied the agreement in determining sleep architecture between the WatchPAT 100 and an in laboratory polysomnogram. The overall agreement in detecting light/deep and REM sleep were $88.6\% \pm 5.9\%$ and $88.7\% \pm 5.5\%$ respectively. OSA severity did not affect the sensitivity and specificity of the algorithm. The Cohen K coefficient for detecting all sleep stages: sleep from wake, REM from NREM sleep and deep from light sleep were 0.48, 0.55, 0.59 and 0.46, respectively. They concluded that analysis of signals from the PAT recorder can detect sleep stages with moderate agreement to more standard techniques in normal subjects and OSA patients.³⁹

There are a few studies looking into the utility of the WatchPAT in the younger population. A pilot study by Serra et al was performed to evaluate the efficiency of the WatchPAT in determining pediatric sleep disordered breathing (PSDB) in 28 children (5-12 years) presenting with symptoms of SDB but with a negative nocturnal pulse oximetry test. The study showed that in these children, the WatchPAT was able to detect sleep disordered breathing in 10/28 (35.7%) using a cut off of PAT Respiratory Disturbance Index (PRDI) of 5 in patients who tested negative during a nocturnal oximetry test. When the threshold for SDB was changed to a PAHI of >1, the number of positive patients for PSDB increased to 17/28 (60.7%).⁴⁰ A study by Su et al. examined 50 children aged 3-11 years with symptoms of snoring and assessed the sensitivity and specificity in the diagnosis of OSA using a PAT portable sleep monitor and compared it to an in-lab polysomnogram as the reference standard. The study found that in the 6-11 year old age group, 14 cases were diagnosed with OSA by the PAT and polysomnogram; however, in the 3-5 year age group, only six children were diagnosed with OSA and there was a significant difference between the PAT and PSG ($p<0.05$).⁴¹ More validation studies in this age group is needed.

IV. Research Methods

A. Outcome Measure(s):

Primary outcome: Peripheral arterial tone apnea-hypopnea index (PAHI) and severity index
Secondary outcomes: Peripheral arterial tone respiratory disturbance index (PRDI),

Oxygen desaturation index (ODI), Sleep staging and sleep time, Oxygen saturation, Heart rate, Body Position

B. Description of Population to be Enrolled:

Inclusion Criteria:

1. Age 4 through 12 years of age.
2. Referral to the CHCO Sleep Lab due to concerns for OSA and presenting with symptoms such as snoring, witnessed apneas, daytime sleepiness, mouth breathing, etc.
3. Informed consent obtained.

Exclusion Criteria:

1. Medical conditions that can affect the tonometer reading such as peripheral vascular disease, cyanotic heart disease, systemic hypertension and sickle cell crisis.
2. Medical conditions that can potentially limit tolerance of the WatchPAT 200 device such as autism spectrum disorder, Trisomy 21 and neurodevelopmental disorders.
3. History of neuromuscular or craniofacial malformation
4. History of current supplemental oxygen use
5. History of current vasoactive, cardiac or seizure medication use
6. Inability or unwillingness to provide informed consent

C. Study Design and Research Methods

This is an investigator-initiated pilot study that evaluates the efficacy of the WatchPAT 200 device in the diagnosis of pediatric OSA. Subjects will be identified through the Children's Hospital Colorado Sleep Clinic and will have already been referred for a clinically indicated sleep study. After IRB approval is obtained, subjects will be recruited through the sleep lab by the research team who fit the inclusion and exclusion criteria. Subjects who appear via chart review to be a good fit will be approached prior to their sleep study to inform them of the research protocol and gauge interest in participation.

For all subjects, the sleep study will be scheduled and equipment set up in a fashion routine to therapeutic sleep studies. The standard of care will not be altered or changed due to participation in the study or not.

Subjects who decide to participate in the research protocol will undergo their normal PSG setup in the sleep lab. Additionally, they will wear the WatchPAT 200 device on their wrist to validate both the PSG and WatchPAT 200 at the same time. The WatchPAT 200 will be placed on the subject's wrist by a registered sleep technician or member of the study team that is familiar with the device. The consenting process will also take place by designated research sleep technicians or members of the study team.

Data to be collected from all subjects include results of baseline/diagnostic polysomnogram (PSG) and sleep parameter indices (apnea-hypopnea index, etc.). Upon completion of the sleep study, the clinically indicated study will be scored by a physician as normal. The PSG will then be scored again by a single-point dedicated sleep technician research scorer to ensure consistent scoring methods between subjects and clinical sleep study scorers. The data collected by the WatchPAT 200 device will be scored through the WatchPAT 200 software installed on a local encrypted and password-protected computer. Additional information that may be collected includes medical history, medications, and basic demographic information.

D. Description, Risks and Justification of Procedures and Data Collection Tools:

The use of the WatchPAT 200 device has very low risk to the subject. This is a closed system that is worn on the wrist and finger that is not invasive to the patient. The device includes connections the EKG leads and other standard markers that are included in a clinical polysomnogram but are

optional and can be removed from the device between subjects. There is a slight risk of irritation of wearing the device as patients will most likely not be used to wearing someone on their wrists during their habitual sleep episodes.

E. Potential Scientific Problems:

There are no potential scientific problems at this time.

F. Data Analysis Plan:

Statistical Analysis plan

Data collected for a participant will be excluded from the analysis if any of the following: 1) WatchPAT 200 sleep time of less than 4 hours, 2) Lab test sleep time of less than 4 hours, 3) poor quality Lab test, consisting of a substantial portion of the Lab test not assessable, as determined by research staff occurred and 4) all WatchPAT 200 channel information not available from the study. The primary goal of the study is to validate and compare two sleep study modalities: 1) WatchPAT 200 and 2) Lab Testing sleep apnea.

Summary statistics of basic demographics on the study population will be calculated. Wilcoxon signed rank test will compare median outcomes of interest (Total AHI, OAHI,etc) between WatchPAT 200 and PSG Lab testing. Spearman's correlation coefficient will be used to measure correlation between WatchPAT 200 and Lab testing. Bland Altman plots will graphically assess modality correlation. Sensitivity and specificity with 95% confidence intervals of WatchPAT 200 will be calculated for three cutoffs of the outcomes (<2, <5, and <10 events/hour) using the PSG lab study as the gold standard. Finally, test agreement on apnea categories will be assessed using Cohen's Kappa statistics fixing OSA diagnosis as dichotomized as none or mild (OAHI <2 events/hour) versus moderate or severe (OAHI \geq 5 events/hour) disease. Other analyses may be conducted on specific strata of participants, based on either patient age or BMI percentile.

Power and Sample Size

Power and sample size were calculated for the primary aim of the study using Power Analysis & Sample Size Software, PASS 15.0 (NCSS, LLC. Kaysville, Utah, USA). The primary aim is to assess whether the PatWatch device agrees with PSG laboratory studies in its ability to detect OSA. For the power analysis OSA diagnosis was dichotomized as non or mild (AHI<4.5) versus moderate or severe (AHI \geq 4.5) disease.

From previous clinical sleep study experience, (from personal review of PSG's performed at the Main Campus of Children's Hospital Colorado in the month of February 2017), investigators anticipate roughly 11 PSG sleep studies per month with about 2 patients diagnosed with OSA.

In a test for agreement between two raters using the Kappa statistic, a sample size of 120 participants achieves 80% power to detect a true Kappa value of 0.95 in a test of H0: Kappa \leq κ_0 vs. H1: Kappa $>$ κ_0 when there are 2 categories with frequencies equal to 0.82 and 0.18. This power calculation is based on a significance level of alpha = 0.05.

Investigators also wished to determine whether the difference of proportions of individuals detected to have OSA between testing modalities was no larger than 5%.

A sample size of 147 participants achieves 80 % power at a significance level of 0.05 using a one-sided non-inferiority test of correlated proportions when the standard proportion is 0.18, the maximum allowable difference between these proportions that still results in non-inferiority (the range of non-inferiority) is 0.05 or 5%, and assuming the actual difference of the proportions is 0.0.

With 17 months enrollment and an enrollment rate of 80%, investigators anticipate enrolling 150 participants to ensure power >80% for each hypothesis test described above.

G. Summarize Knowledge to be Gained:

We hope to gain the knowledge that the WatchPAT 200 device will be able to detect OSA in children 4-12 years of age with comparable accuracy with an in-laboratory PSG.

H. References:

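### Planned accuracy covers only nights on which the WatchPAT worked, and no planned analysis counts the nights on which it did not

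*Combined protocol and SAP*

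**What the plan says.** Section IV.F lists four grounds for removing a child from the analysis. Two concern the device under test: data are "excluded from the analysis if any of the following: 1) WatchPAT 200 sleep time of less than 4 hours", and item 4 reads "4) all WatchPAT 200 channel information not available from the study". Two concern the reference: "2) Lab test sleep time of less than 4 hours", and a PSG that research staff judge to be of poor quality. Section IV.C says that the WatchPAT data are scored by the device's own software, so the sleep time used in item 1 is an output of the device.

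The same section then plans demographic summaries, a Wilcoxon test, Spearman correlation, Bland-Altman plots, sensitivity and specificity with 95% confidence intervals at three cutoffs, and Cohen's kappa. The Wilcoxon sentence is: "Wilcoxon signed rank test will compare median outcomes of interest (Total AHI, OAHI,etc) between WatchPAT 200 and PSG Lab testing". Sleep time is not named there, but section IV.A lists among the secondary outcomes "Oxygen desaturation index (ODI), Sleep staging and sleep time, Oxygen saturation, Heart rate, Body Position", and Aim 4 is "To evaluate the accuracy of the WatchPAT 200 device in determining sleep architecture compared to an in-laboratory polysomnogram".

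The hypothesis in section I is that the device detects OSA in children aged 4 to 12 as effectively as attended PSG.

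**The concern.** A child whose PSG is valid but whose WatchPAT night failed leaves the analysis, and no planned table shows it. The accuracy figures then answer how well the device classifies when it works. The hypothesis in section I is wider, and in young children wearing a wrist and finger device overnight the share of nights that work is part of the answer. Two devices with the same usable-night sensitivity, one failing in 1% of children and the other in 15%, would look identical under this plan.

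A smaller question follows from the same rule. Because exclusion 1 selects on scored sleep time, and sleep time is a declared secondary outcome, any sleep-time comparison is made on pairs selected partly by one of the two measurements.

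**Working it through.** **1. Which nights each rule removes.** Let P be PSG sleep time and W the WatchPAT's scored sleep time.

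- P at least 4 h, W at least 4 h: kept, subject to items 3 and 4.
- P at least 4 h, W under 4 h: removed by exclusion 1 alone. W − P is always negative.
- P under 4 h, W at least 4 h: removed by exclusion 2 alone. W − P is always positive.
- Both under 4 h: removed by both rules.

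The second group, plus children removed by item 4 alone who have a valid PSG, are the device failures. The planned analyses in section IV.F contain no category, count or sensitivity analysis for them.

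**2. What counting them would do to accuracy.** Let TP and FN be the true positives and false negatives among usable nights, and F the PSG-positive children whose WatchPAT night failed. Counting failures as not correctly classified:

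sensitivity (all valid PSG) = TP / (TP + FN + F) = usable-night sensitivity × (1 − f), where f = F / (TP + FN + F).

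Specificity has the same form among PSG-negative children. The documents give no value for f. Two illustrations:

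- Power and Sample Size uses an OSA proportion of 0.18 and an enrolment of 150, so 0.18 × 150 = 27. One, two or three failures among these give 26/27 = 0.963, 25/27 = 0.926 and 24/27 = 0.889. The 0.18 belongs to a split at AHI 4.5, which is not one of the planned cutoffs, so 27 is only a guide.
- With an assumed usable-night sensitivity of 0.90, assumed failure shares of 5%, 10% and 20% give 0.90 × 0.95 = 0.855, 0.90 × 0.90 = 0.81 and 0.90 × 0.80 = 0.72.

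**3. Size of the sleep-time effect.** All inputs are assumed. In 4,000,000 simulated pairs per scenario, P is normal and W = P + bias + normal error, in minutes, for full-length recordings. The table shows the shift in mean W − P caused by adding exclusion 1 to exclusion 2.

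| P mean/SD, error SD | bias −30 | bias 0 | bias +30 |
|---|---|---|---|
| 400/75, 60 | +6.3 | +3.6 | +1.8 |
| 400/75, 45 | +3.1 | +1.5 | +0.6 |
| 420/60, 45 | +1.5 | +0.6 | +0.2 |

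Exclusion 1 removed no over-reading in any scenario. In the first row it dropped 7.6%, 3.8% and 1.6% of pairs, and the lower limit of agreement moved from −148 to −135, −118 to −110 and −88 to −83. With no true bias and 150 children, the Wilcoxon false-positive rate was 9.4%, 6.4% and 5.9% for the three rows with exclusion 1, against 5.3%, 4.6% and 5.6% without it (Monte Carlo standard error about 0.4 points).

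The top of that range is at the edge of plausibility. Section III says of 28 adults: "It also provided a reasonably accurate estimation of sleep and wakefulness", with 89% agreement. The remaining 11% of an assumed 480 to 540 min recording is 0.11 × 480 = 52.8 to 0.11 × 540 = 59.4 min, the most the mean absolute sleep-time error could be at that agreement. The +6.3 scenario has a mean absolute error of 53.7 min.

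**4. Two changes to the model (400/75, total error SD 60, bias 0).**

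- Error split equally between PSG and WatchPAT: the plan's rules give a mean difference of about 0 (0.1 min or less), and exclusion 2 alone gives about −1.5 min.
- All error in the WatchPAT, and 5% of devices recording a random 0 to 60% of the night: the plan's rules give about +2.8 min with lower limit −113; exclusions 2 and 3 alone give −14.1 and −185. The full-length truth is 0 and −118.

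**The case against.** The strongest reply is that nothing here disturbs the primary outcome. PAHI accuracy among usable recordings is a legitimate quantity, a short or empty recording cannot support a PAHI, and the study calls itself a pilot. That stands, and exclusion 1 should stay in the main accuracy analysis. The remaining gap is that failures go uncounted.

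Four stronger readings are tempting, and the documents do not support them.

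- A reader might infer that the planned sensitivity, specificity or kappa are biased. The documents give no failure rate and no link between failure and PAHI error, so neither the presence nor the direction of bias can be shown.
- A reader might infer that the sleep-time comparison is materially distorted, or that exclusion 1 does nothing about poor wear. Section IV.F does not name sleep time among the compared outcomes, and exclusion 2 is the mirror rule on the PSG side. The shift nearly vanishes if the two methods share the error, and exclusion 1 removes most of the partial-wear artefact. Any effect on sleep staging is indirect and has not been quantified.
- A reader might take item 4 to discard a usable PAHI whenever one channel is lost, including the "optional snoring level and body position discrete states from an external integrated snoring and body position (SBP) sensor" described in section II. Read literally, item 4 means that no WatchPAT data exist, where removal is unavoidable.
- A reader might infer that the study becomes underpowered, because 150 are enrolled and 147 are needed for the non-inferiority test. That is a separate attrition question and small at the margin: scaling from 80% at 147, 146 analysed gives about 79.8% power. The kappa calculation needs 120, which leaves 150 − 120 = 30 spare.

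**Conclusion.** The point holds as a minor one. Exclusion 1 and item 4 make the planned accuracy figures conditional on the device having worked, and no planned analysis shows how many children with a valid PSG had an unusable WatchPAT night. This rests on the text alone. Its numerical size depends on a failure rate that the documents do not give: the worst-case factor on sensitivity or specificity is one minus the failure share in that group, so 1.00 to 0.90 for an assumed 0 to 10%.

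For sleep time, it is certain that exclusion 1 can remove only under-readings among children with PSG sleep of at least 4 h. The resulting shift is about 0 to 6 min for full-length recordings, depends on the assumed error model, and may be negligible. Neither finding shows bias in the primary usable-night estimates.

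**What to change.** - Keep the usable-recording analysis, with all four exclusions, as the main accuracy analysis.
- Add a supplementary accuracy analysis in all children with a valid PSG. Apply exclusions 2 and 3 before the WatchPAT result is opened, count each unusable WatchPAT night as not correctly classified, and label the result a worst-case bound.
- Report the proportion of failed WatchPAT nights by reason (scored sleep under 4 h, no channel data) and by PSG OSA status.
- If sleep time is compared, show the agreement both with and without exclusion 1. Neither version is free of bias: the first cuts off under-readings and the second lets in partly worn nights. Nights with no WatchPAT data cannot enter either version and belong in the failure count.
- As a matter of wording only, state whether item 4 means that all channels are missing or any channel.

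The cost is some SAP text and one extra set of tables from data collected on the same night. The downside is that the supplementary accuracy figure cannot exceed the main one and could be misread as the headline unless it is clearly labelled.

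### PAHI has no fixed PSG reference: the plan names both total AHI and OAHI for comparison, runs kappa on OAHI (<2, ≥5), and powers on AHI at 4.5.

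*Combined protocol and SAP*

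**What the plan says.** **Device side.** Section II (Background and Significance) lists the clinical outputs as "1. PAT apnea-hypopnea index (PAHI), 2. PAT respiratory disturbance index (PRDI), 3. PAT sleep staging identification (PSTAGES"), with optional snoring and body position. It says that "The device then indirectly detects apnea and hypopnea via selectively measuring peripheral arterial volume changes", and gives the mechanism as "obstruction-induced transient elevations of sympathetic tone which have been associated with arousals from sleep". No output is labelled obstructive or central, and central events are not mentioned anywhere.

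**Outcome and aims.** Section IV.A gives the primary outcome as "Peripheral arterial tone apnea-hypopnea index (PAHI) and severity index". Aim 1 assesses accuracy "through measurement of the peripheral arterial tone apnea hypopnea index (PAHI) in children 4-12 years of age". Neither names the PSG index that PAHI is judged against. Aim 2 uses OAHI, with moderate to severe disease starting at 5 events/hour.

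**Analysis and power (IV.F).** The paired test is described as "Wilcoxon signed rank test will compare median outcomes of interest (Total AHI, OAHI,etc) between WatchPAT 200 and PSG Lab testing". Sensitivity and specificity are planned at 2, 5 and 10 events/hour for outcomes that are not named. Kappa compares OAHI below 2 with OAHI of 5 or more. The Power and Sample Size text reads "For the power analysis OSA diagnosis was dichotomized as non or mild (AHI<4.5"), against 4.5 or more.

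**The concern.** A validation study needs one stated reference value for its primary device measure. Here the primary measure is PAHI, and the reference is total AHI in one place, OAHI in others and unnamed in the rest. The plan itself treats total AHI and OAHI as separate quantities, so in any child where they differ PAHI can agree with at most one of them. An OAHI comparison between device and PSG also has no labelled counterpart among the listed device outputs.

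Three things are at stake. A disagreement in the report could reflect either device error or a mismatch of indices. With no named reference, the index could be chosen after the results are seen. And the sample size was justified for a classification (AHI at 4.5) that the kappa analysis does not use.

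**Working it through.** **1. The plan's own figures.** The category frequency of 0.18 matches the expected 2 OSA diagnoses in 11 studies per month: 2/11 = 0.18. The index and cut behind those diagnoses are not stated. The kappa sample size follows

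N = [(z₀.₉₅·τ(κ₀) + z₀.₈₀·τ(κ₁)) / (κ₁ − κ₀)]²,

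where τ is the large-sample standard error of kappa per observation, with both margins at 0.82/0.18, and κ₁ = 0.95. The null κ₀ appears only as a symbol. Assuming κ₀ = 0.80 and a one-sided 0.05 test, N = 121 against the stated 120 (power at 120 is 79.8%). The stated size is therefore consistent with a null of 0.80, but that value is inferred. The formula takes only frequencies, so changing the index label alone does not change N.

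**2. Definitions side by side.**

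| Place | PSG index | Cut (events/hour) |
|---|---|---|
| Aim 1; primary outcome | not named | none |
| Aim 2 | OAHI | 2 and 5 |
| Wilcoxon | total AHI, OAHI, others | none |
| Sensitivity, specificity | not named | 2, 5, 10 |
| Kappa | OAHI | <2 versus ≥5 |
| Power | AHI | 4.5 |

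Kappa and power disagree on both the label and the cut.

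**3. Direction.** Write total AHI = OAHI + C, with C the non-obstructive index, C ≥ 0.
- If PAHI registers C, then at a given cut the OAHI comparison gains false positives: children with OAHI below the cut and OAHI + C at or above it.
- If PAHI does not register C, the same children become false negatives against total AHI.

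In both cases one comparison is not like for like. The documents do not say which case applies.

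**4. Illustrative size.** No central-event rate is given, so the inputs here are assumptions: PAHI equals total AHI without error; OAHI is lognormal with median 1.5/h and 18% at or above 5/h (applying the plan's 0.18 to that cut), so the log-scale SD is ln(5/1.5)/0.915 = 1.32; C is exponential and independent of OAHI. Simulation of 2,000,000 children per scenario, with PSG OAHI as reference, gives:

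| Mean central index (/h) | Specificity at 2/h | Kappa, single 5/h cut | Kappa, PSG OAHI 2 to 5 left out |
|---|---|---|---|
| 0.25 | about 93% | 0.96 | above 0.999 |
| 0.5 | 83% | 0.92 | 0.999 |
| 1.0 | 64% | 0.81 | 0.96 |
| 2.0 | 42% | 0.56 | 0.76 |

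The last column is the literal reading of the plan's kappa, with PAHI ≥5 as test-positive. At a mean of 1.0/h, with OAHI medians from 1 to 2/h, the single-cut kappa runs from 0.85 to 0.76, and the literal version is 0.96 to 0.97. In the reverse case (PAHI tracks obstructive events only, reference total AHI, median 1.5/h, mean 1.0/h), sensitivity at 5/h is about 73%.

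**5. A check without the distributional model.** Take a device with kappa 0.95 and prevalence 0.18, so each discordant cell is 0.18 × 0.82 × 0.05 = 0.00738. Suppose a further 5% of all children are below the cut on OAHI and above it on the device.
- Observed agreement: 1 − 2 × 0.00738 − 0.05 = 0.93524.
- Device-positive share: 0.23.
- Chance agreement: 0.18 × 0.23 + 0.82 × 0.77 = 0.6728.
- Kappa: (0.93524 − 0.6728)/(1 − 0.6728) = 0.80.
- Specificity: (0.82 − 0.00738 − 0.05)/0.82 = 93%.

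The 5% is again an assumption.

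**The case against.** A reader might infer that central events will be counted as device error. The documents do not support that. They never mention central events, and the only mechanism they describe is obstructive. If PAHI misses central events, OAHI is the matched reference and the mismatch moves to total AHI. This objection stands, and it rules out pairing PAHI with total AHI alone in the agreement analyses.

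A false positive against OAHI is also a real error for a test of obstructive sleep apnea, whatever its cause. It is a limitation to report and should not be called bias. That stands too, and it is why OAHI should remain the primary reference.

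A reader might infer that power was computed on total AHI. The power text says only AHI, while the analysis text writes total AHI when it means that, so the label may be loose wording for OAHI. The difference in label is in the text; a difference in the quantity used is not established. The difference between a cut of 4.5 and cuts of 2 and 5 does not depend on this.

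A reader might also conclude that a perfect device could fail the kappa test. That needs a null of 0.80, which is inferred, and under the literal kappa wording it needs a mean central index near 2/h in this model. No figure in the documents supports such a rate.

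Finally, the plan already lists both PSG indices, so both comparisons may be intended. What is missing is the statement of which is primary and how each pairs with PAHI.

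**Conclusion.** The point holds as an inconsistency in the plan. Its text shows that no obstructive-only device index is listed, that the PSG reference for PAHI is not fixed across analyses, and that the power calculation and the kappa analysis classify children differently in cut and in index label. It follows that at least one of the total AHI and OAHI comparisons is not like for like in any child where the two differ.

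Neither the direction nor the size of the effect can be set from the documents. Under the assumptions in the working, the effect is small at a low central-event rate and large for specificity at the 2/h cut at higher rates. For kappa it depends heavily on whether children with OAHI of 2 to 5 are kept in. These figures show a possible range and are not a forecast for this study.

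**What to change.** 1. Name PSG OAHI, already the Aim 2 reference, as the primary reference for PAHI. For sensitivity, specificity and kappa, define test-positive as PAHI at or above the cut and reference-positive as OAHI at or above the same cut. For kappa, a single common cut also gives a place to children with OAHI of 2 to 5, whom the current wording leaves out.
2. Run Wilcoxon, Spearman and Bland-Altman for PAHI against both OAHI and total AHI.
3. Repeat the accuracy and kappa tables against total AHI as a sensitivity analysis, so that index mismatch can be told from device error. State how non-obstructive events on PSG are handled and, if known, whether PAHI registers them.
4. Restate the power paragraph on the index and cut of the kappa analysis in place of AHI 4.5, and confirm that the 0.18 frequency refers to that definition.

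The cost is a wording change and one extra set of tables. The planned research re-scoring of each PSG should supply both indices. No sample size changes on this point alone; if step 4 shows that 0.18 belongs to another definition, the power inputs would need a fresh look.
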